# **Safety Endpoints**

The primary safety analysis will include Grade 2 or higher clinical and laboratory events that occur from the initial injection to 12 weeks after the last injection among participants who receive at least one injection. Secondary safety analyses will include the same definition applied over the oral phase only (week 0 to week 5) and the aggregate oral+injectable+follow-up period.

To assess safety, the number and the percent of participants experiencing each safety endpoint will be tabulated by study arm. Each participant will contribute once in each category (for example, only for the highest severity AE for each participant) for the calculation of event rates. Exact binomial confidence intervals will be calculated for each safety endpoint for each arm and Fisher's exact test used to test for differences in event rates between the two arms. No formal treatment comparisons will be performed in this study, so any p-values that are calculated should only be used as a descriptive statistic. No formal multiple comparison adjustments will be employed for safety endpoints.

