### 2.0 STUDY OBJECTIVES AND DESIGN

#### 2.1 Primary Objective

Evaluate the safety and tolerability of the injectable agent, GSK1265744 long acting (744LA) injectable (800 mg dose administered at three time points at 12 week intervals) through Week 41 in HIV-uninfected men and women.

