### 5.10 Week 41 – Primary Endpoint Visit

Administrative, Behavioral, and Regulatory Procedures

- Locator information
- HIV counseling
- Offer condoms and lubricant
- Behavioral assessment

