# 7.1.1 Primary Endpoint

Safety endpoint: Proportion of participants experiencing any Grade 2 or higher clinical AEs and laboratory abnormalities that occur from the initial injection to Week 41 among participants who receive at least one injection (injectable phase only)

Tolerability endpoint: Proportion of participants who receive at least 1 injection and who discontinue receiving injections prior to the full course of 3 injections due to intolerability of injection (including but not limited to ISR), frequency of injections, burden of study procedures, or any AE.

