The primary safety endpoint is the proportion of participants experiencing any Grade 2 or higher clinical AEs and laboratory abnormalities that occur from the initial injection to 41 weeks among participants who receive at least one injection. The precision with which the true event rate can be estimated from the observed data depends on the underlying true event rate and the sample size. Table 4 shows the two-sided 95% confidence intervals for the true event rate based on various values for the observed event rates, given the sample size of 120 in 744LA arm and 40 in placebo arm. Calculations are done using the score test method.

Table 4. Two-sided 95% confidence intervals based on observing a particular rate of event for the 744LA arm (n=120) and the placebo arm (n=40)

Observed Event	95% CI (744LA arm)	95% CI (Placebo arm)
Rate (%)		
0	(0, 3.1)	(0, 8.8)
2.5	(0.9, 7.1)	(0.4, 12.9)
5	(2.3, 10.5)	(1.4, 16.5)
10	(5.8, 16.7)	(4, 23.1)
15	(9.7, 22.5)	(7.1, 29.1)
20	(13.8, 28)	(10.5, 34.8)
25	(18.1, 33.4)	(14.2, 40.2)

The safety and toxicity rates of people using 744LA and the rates for those using placebo will not be formally compared. A sample size of 160 participants (120 in 744LA and 40 in placebo) assuming 90% retention rate per year will assure with 82% power that a 95% confidence interval for the difference between the study drug and placebo safety and toxicity rates has an upper limit no more than 10% when the true toxicity rates for 744LA and placebo are both 5%. Table 5 displays two-sided 95% confidence interval for different assumptions on the safety and toxicity rates in the active product and placebo arms for a study of this sample size.

Table 5: Two-sided 95% Confidence Intervals for the Difference between 744LA and Placebo Safety Rates (n=120 in the 744LA arm and n=40 in the placebo arm)

Assumed rate	Assumed rate in 744LA arm											
in placebo arm	1% 5%		7.5%	10.0%	12.5%	15.0%						
1%	(-3.6, 3.6)	(-1, 9)	(0.9, 12.1)	(2.8, 15.2)	(4.8, 18.2)	(6.9, 21.1)						
5%	-	(-7.8, 7.8)	(-5.7, 10.7)	(-3.6, 13.6)	(-1.5, 16.5)	(0.7, 19.3)						
7.5%	-	1	(-9.4, 9.4)	(-7.3, 12.3)	(-5.1, 15.1)	(-2.9, 17.9)						
10.0%				(-10.7,	(05.105)	( ( 2 1 ( 2 )						
	-	-	-	10.7)	(-8.5, 13.5)	(-6.3, 16.3)						
12.5%					(-11.8,							
12.5 /0	-	-	-	-	11.8)	(-9.6, 14.6)						
15.0%						(-12.8,						
15.0 / 0	-	-	-	-	-	12.8)						

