### 7.5 Blinding

Study site staff, with the exception of the site Pharmacist of Record or their designee, and participants will be blinded to the random assignments. Blinding will be maintained until the last participant enrolled in to the active drug arm has completed their Week 41 visit (the time point of the primary endpoint of the study), and when all data related to the Week 41 visit has been entered into the database, as well as cleaned and verified. At a specified time directed by the HPTN SDMC, participants will be unblinded to their treatment assignment, and participants in the placebo arm will no longer need to be followed. Participants in the active study product arm will continued to be followed for 52 weeks after their last injection. In addition, as noted in Section 5.16, an Investigator can request unblinding to the CMC in the event that a participant becomes infected with HIV during the study, and the CMC will assist in the treatment of the participant's HIV infection.

NOTE: Samples may be unblinded in the HPTN Pharmacology Laboratory (only), so the relevant assays are only performed on participants who received the study product.

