Appendix II: Schedule of Procedures and Evaluations – For Participants Who Complete Two Injections Only

Appendix II: Schedule		idi es dire	Livuluulo			se Follow-up	inpiece 1	Wo Hijeedic	ins only
	Week 5 First Injection	Week 6, 9, 13 Safety	Week 17 Second Injection	Week 18, 23 Safety	Week 29 Follow Up	Week 41 Follow Up	Week 53 Follow Up	Week 65 Follow Up	Week 69 Final
ADMINISTRATIVE, BEHAV	VIORAL, RE	GULATOI	RY						
Locator information	X	X	X	X	X	X	X	X	
HIV counseling	X	X	X	X	X	X	X	X	X
Offer condoms and lubricant	X	X	X	X	X	X	X	X	X
Acceptability assessment (Week 6 and 18 only)		X		X					
Behavioral assessment	X		X		X	X	X	X	
CLINICAL EVALUATIONS	& PROCED	URES							
History, con meds, physical exam 	X	X	X	X	X	X	X	X	X
ECG 		X		X					
Blood collection	X	X	X	X	X	X	X	X	X
Urine collection for GC/CT testing men and women 					X		X		
Urine pregnancy testing 	X		X		X	X	X	X	X
Rectal swab for GC/CT testing men and women 					X		X		
Vaginal swab for GC/CT testing  (Optional alternate collection for women if urine not used)					X		X		
Administer injection 	X		X						
ISR evaluation		X		X					
LOCAL LABORATORY EVALUATIONS									
HIV testing 	X	X	X	X	X	X	X	X	X
CBC with differential	X	X	X	X	X				
Chemistry testing 	X	X	X	X	X				

		Injection And Tail Phase Follow-up							
	Week 5 First Injection	Week 6, 9, 13 Safety	Week 17 Second Injection	Week 18, 23 Safety	Week 29 Follow Up	Week 41 Follow Up	Week 53 Follow Up	Week 65 Follow Up	Week 69 Final
LFTs (AST, ALT, total bilirubin, alkaline phosphatase)	X	X	X	X	X	X	X	X	X
Syphilis serologic testing men and women 					X		X		
Urine/vaginal swab GC/CT testing men and women 					X		X		
Plasma storage 	X	X	X	X	X	X	X	X	X
Plasma storage for Pharmacology testing 	X	X	X	X	X	X	X	X	X

SEE FOOTNOTES FOR APPENDIX I

Appendix III: Schedule of Procedures and Evaluations – For Participants Who Complete One Injection Only

Appendix III: Schedule of Pro	cedures und	L valuation		And Tail Phase		e one inject	Jon Omy
	Week 5 First Injection	Week 6, 9, 13 Safety	Week 17 Follow Up	Week 29 Follow Up	Week 41 Follow Up	Week 53 Follow Up	Week 57 Final Visit
ADMINISTRATIVE, BEHAVIORAL	, REGULATO	RY				 	
Locator information	X	X	X	X	X	X	X
HIV counseling	X	X	X	X	X	X	X
Offer condoms and lubricant	X	X	X	X	X	X	X
Tolerability/Acceptability Assessment (Week 6 only)		X					

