Behavioral assessment	X		X	X	X	X	
CLINICAL EVALUATIONS & PROC	CEDURES	1		1	1	1	
History, con meds, physical exam 	X	X	X	X	X	X	X
ECG 		X					
Blood collection	X	X	X	X	X	X	X
Urine collection for GC/CT testing men and women 				X		X	
Urine pregnancy testing 	X		X	X	X	X	X
Rectal swab for GC/CT testing men and women 				X		X	
Vaginal swab for GC/CT testing  (Optional alternate collection for women if urine not used)				X		X	
Administer injection 	X						
ISR Evaluation		X					
LOCAL LABORATORY EVALUATIONS							
HIV testing 	X	X	X	X	X	X	X
CBC with differential	X	X	X				
Chemistry testing 	X	X	X				
LFTs (AST, ALT, total bilirubin, alkaline phosphatase)	X	X	X	X	X	X	X

		Injection And Tail Phase Follow-up						
	Week 5 First Injection	Week 6, 9, 13 Safety	Week 17 Follow Up	Week 29 Follow Up	Week 41 Follow Up	Week 53 Follow Up	Week 57 Final Visit	
Syphilis serologic testing men and women 				X		X		
Urine/vaginal swab GC/CT testing men and women 				X		X		
Rectal swab GC/CT testing 				X		X		
Plasma storage 	X	X	X	X	X	X	X	
Plasma storage for Pharmacology testing 	X	X	X	X	X	X	X	

SEE FOOTNOTES FOR APPENDIX I

Appendix IV: Schedule for Additional Laboratory Procedures for Enrolled Participants who have a Reactive Positive HIV Test Result (HIV Confirmation Visit – to be performed on a

different day from the initial reactive/positive sample)

	HIV Confirmation Visit
ADMININISTRATIVE, BEHAVIORAL, REGULATORY	
Locator information	X
Offer condoms and lubricant	X
HIV counseling	X
CLINICAL EVALUATIONS AND PROCEDURES	
Blood collection	X
LOCAL LABORATORY EVALUATIONS	
HIV testing 	X
CD4 cell count	X
HIV resistance testing 	$X^2$
Plasma storage 	X

<sup>1 The HIV testing algorithm for the HIV Confirmation Visit is provided in the SSP Manual. If HIV rapid testing is included in the HIV testing algorithm, this testing may be performed in the clinic or the laboratory.

<sup>2 Sites may collect specimens for resistance testing at a local laboratory to assist with clinical management; results from resistance testing performed at local laboratories will not be reported to the SDMC. Stored plasma may not be used real-time/local resistance testing.

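### The primary safety endpoint ends at Week 41 in Sections 7.1.1 and 7.2 but 12 weeks after the last injection in Section 7.6.2; the two differ for participants who stop after one or two injections

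*Protocol*

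**What the plan says.** **Endpoint definition.** Section 7.1.1 takes the proportion of participants with Grade 2 or higher clinical events and "laboratory abnormalities that occur from the initial injection to Week 41 among participants who receive at least one injection (injectable phase only"). Section 7.2 repeats the definition for the same people: "from the initial injection to 41 weeks among participants who receive at least one injection". The primary objective in Section 2.1 runs "through Week 41 in HIV-uninfected men and women".

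**Analysis.** Section 7.6.2, under Safety Endpoints, also restricts the primary safety analysis to participants with at least one injection, but includes "Grade 2 or higher clinical and laboratory events that occur from the initial injection to 12 weeks after the last injection". Its secondary safety analyses cover the oral phase and the whole study period, so neither uses one of the two windows above.

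**Context.** Section 5.10 labels Week 41 the "Primary Endpoint Visit", and Section 7.5 ties unblinding to it. Section 5.15 follows participants who stop after one or two injections to Week 57 or Week 69. Placebo follow-up may end sooner, at the planned unblinding, which comes after the last active participant's Week 41 visit.

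**Laboratory schedules.** In Appendix II ("For Participants Who Complete Two Injections Only") the rows for "CBC with differential" and chemistry end at Week 29. In Appendix III, for one injection, they end at Week 17. Liver tests, history and examination continue in both.

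**The concern.** Section 7.6.2 defines the primary analysis population as everyone injected, so early stoppers count in the primary proportion. They are also expected: early discontinuation is itself the primary tolerability endpoint, and Appendix VI requires permanent discontinuation for several toxicities.

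Take a participant who receives one injection and has a first Grade 2 event at Week 25. Section 7.1.1 counts that person as a primary endpoint event and Section 7.6.2 does not. Two analysts could each follow the protocol and report different primary proportions and confidence intervals from the same data.

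This is not detail properly left to an analysis plan. Two rules are stated, and a plan that follows one departs from the other. Because early stopping can be caused by adverse events, the length of the 7.6.2 window can also depend on a participant's own outcome.

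**Working it through.** **1. Window ends.** Injections are at Weeks 5, 17 and 29 (Section 2.4).

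| Injections received | 7.6.2 window ends | Length from Week 5 | Length under 7.1.1 | Weeks in dispute |
|---|---|---|---|---|
| One | 5 + 12 = Week 17 | 12 | 41 − 5 = 36 | 41 − 17 = 24 |
| Two | 17 + 12 = Week 29 | 24 | 36 | 41 − 29 = 12 |
| Three | 29 + 12 = Week 41 | 36 | 36 | 0 |

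Section 7.2 says 41 weeks, which read literally from the first injection would be Week 46 (5 + 41). Study Week 41 is clearly meant.

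**2. Assumptions for size.** The protocol gives no stopping rate and no expected Grade 2 event rate, so these inputs are assumed: 36-week event proportion p = 25%; share stopping early s = 10%, half after one injection and half after two; constant hazard; and f, the share of stoppers already counted before the disputed weeks, = 0.

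**3. Shift with complete laboratory detection to Week 41.**
- 12-week proportion: 1 − (1 − p)^(1/3) = 1 − 0.75^(1/3) = 9.14%.
- 24-week proportion: 1 − (1 − p)^(2/3) = 1 − 0.75^(2/3) = 17.45%.
- Shift = (1 − f) × [s/2 × (p − p12) + s/2 × (p − p24)] = 0.05 × 15.86 + 0.05 × 7.55 = 1.17 points, or 0.0117 × 132 ≈ 1.5 people.
- With f = 0.5 it is 0.59 points, about 0.8 people.

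**4. Shift under the current schedules.** CBC and chemistry are not scheduled in the disputed weeks, so a Week 41 rule would miss some first events there. Let q be the share of the hazard that is non-liver laboratory events found only by routine testing (assumed 10% to 50%), λ = −ln(0.75)/36, and T = 12 or 24.
- miss(T) = exp(−λT) × [exp(−(1 − q)λ(36 − T)) − exp(−λ(36 − T))].
- q = 10%: 0.05 × 1.45 + 0.05 × 0.72 = 0.11 points.
- q = 50%: 0.05 × 7.55 + 0.05 × 3.68 = 0.56 points.
- Net shift: 1.17 − 0.56 = 0.61 to 1.17 − 0.11 = 1.06 points, or about 0.8 to 1.4 of 132 people.

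**5. Between arms, with complete detection and p = 25%.** Equal stopping and event rates give a change of 0. Stopping of 10% in one arm against 5% in the other gives 1.17 − 0.585 = 0.59 points.

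**6. Yardstick.** Table 4 gives a 95% interval of 18.1 to 33.4 for an observed 25% of 120. The Wilson score formula reproduces it: centre (0.25 + 3.84/240)/(1 + 3.84/120) = 25.8%, half-width 7.7 points. The interval is 33.4 − 18.1 = 15.3 points wide.

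**The case against.** **The texts can be reconciled.** Section 7.6.2 refers to the last injection without saying whose, while the follow-up rules speak of participants' own last injections. If the scheduled Week 29 dose is meant, 12 weeks later is Week 41 for everyone. This reading is possible but strained: the sentence expressly includes people with a single injection, and the CBC and chemistry rows in Appendices II and III stop exactly 12 weeks after the individual's own last dose. At best the sentence is ambiguous, and it would need the same edit.

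**Some of the supporting sections are weak.** This stands in part. Section 5.10 describes the full-course visit and Section 7.5 fixes the timing of unblinding; neither sets an individual's counting window. The conflict rests on 7.1.1 and 7.2 against 7.6.2.

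**The effect is minor.** This stands. Section 1.4 reports median injection site reaction durations of about 5 days for pain and erythema and 22 days for nodules, so a full-course hazard probably overstates events in people no longer injected. Section 7.6.2 makes no formal treatment comparison, and its aggregate analysis still includes later events.

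**Stronger readings.** A reader might infer that the mismatch biases the comparison for or against 744LA. The protocol gives no stopping or event rates by arm, so no direction follows. A reader might also infer that outcomes of early stoppers go unobserved to Week 41. They do not: visits, liver tests and adverse event recording continue, and only scheduled non-liver laboratory testing lapses.

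**Conclusion.** The inconsistency is real. The protocol states two primary safety windows for one population, they disagree for anyone who stops after one or two injections, and no rule of precedence is given.

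Its numerical weight is small. In the assumed case the primary proportion in an arm changes by about 0.6 to 1.1 points under the current schedules, with 1.17 points as the ceiling for that case, against a Table 4 interval about 15 points wide. Higher stopping or event rates would enlarge the shift; prior events among stoppers or a lower hazard off injections would shrink it. No alpha or power statement changes. The case for correcting it is that a primary endpoint should have one definition, settled before unblinding.

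**What to change.** **Change.** In Section 7.6.2, Safety Endpoints, replace the end of the primary window with Week 41 and keep the restriction to participants with at least one injection. It then matches 2.1, 7.1.1 and 7.2. If an on-product view is wanted, report the window ending 12 weeks after each participant's own last injection as a sensitivity analysis.

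**Cost.** One sentence. No new visits are needed, because early stoppers already attend at Week 41.

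**Optional.** Deal with the laboratory gap in one of two ways:
- Add CBC and chemistry at visits that already draw blood: Week 41 in Appendix II, and Weeks 29 and 41 in Appendix III. This means editing both appendices and adds one panel per two-injection stopper and two per one-injection stopper.
- State that non-liver laboratory ascertainment is incomplete for early stoppers after Week 29 or Week 17. This costs one sentence.

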#### 2.4.2 Study Duration

This study will be approximately 2 years in length. Accrual will require approximately 16-24 weeks (4-6 months). Study participants will receive oral tablets for 4 weeks, followed by a one week washout period, followed by receipt of three injections over 24 weeks (6 months). Participants in the active study product arm will be followed for 52 weeks following their last injection. Participants in the placebo arm will be followed until 52 weeks after their last injection or until the last participant in the active study product arm completes their Week 41 visit, whichever comes first, at which time the study will be unblinded to assess the primary endpoint. When all procedures related to unblinding are completed, participants in the placebo arm will no longer be followed.

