# **5.16** Planned Unblinding of Study Participants

When the last participant on the active study product arm completes their Week 41 visit, and when all corresponding procedures at the HPTN SDMC, LC, and LOC have been completed, the study will be unblinded. Participants will be unblinded at their next study visit following final confirmation from the HPTN SDMC that all corresponding unblinding procedures have been completed. Participants in the placebo arm will no longer be required to complete any further follow-up visits once they have been unblinded. Active study product arm participants will complete their follow-up per the appropriate Schedule of Evaluations and Procedures.

As previously noted, due to differences in timing of study initiation across the participating sites, as well as the ratio of active product arm vs. placebo arm participants being enrolled, it is likely that some placebo participants will complete their full follow-up visit schedule.

Additional information will be outlined in the SSP Manual.

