# 7.1.2 Secondary Endpoints

- Proportion of participants who discontinue either oral or injectable study product for reasons
  of toxicity, tolerability, or acceptability prior to completion of the full oral and injectable
  phases
- Proportion of participants experiencing Grade 2 or higher clinical AEs and laboratory abnormalities during 52 weeks following final injection (safety) and any AE that leads to discontinuation (tolerability) during the aggregate oral and injectable phases
- Proportion of participants experiencing Grade 2 or higher clinical AEs and laboratory abnormalities (safety) and any AE that leads to discontinuation (tolerability) in the oral phase and washout period
- Plasma drug levels of GSK1265744 at designated time points after each injection of 744LA
- Plasma drug levels of GSK1265744 at designated time points after each injection of 744LA stratified by age, gender, race, ethnicity, weight, BMI, and smoking status
- Proportion of participants willing to use an injectable agent such as the study product for HIV prevention in the future
- Change from enrollment of self-reported sexual behavior (number of sexual partners, episodes of unprotected anal and/or vaginal intercourse) during the study period using a standardized assessment tool
- Number of incident HIV infections through the study period, including number with treatment emergent resistance
- Proportion of injectable hormonal-contraception-using female participants who reach a safety or tolerability endpoint as defined above

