# 7.3 Accrual, Follow-up, and Retention

A total of 176 participants will be enrolled in approximately 16 to 24 weeks. Study participants will receive oral tablets for 4 weeks, followed by a 1 week wash out period, followed by receipt of injections at 3 time points over 24 weeks. Participants in the active drug arm will be followed for 52 weeks (12 months) after their last injection. Participants in the placebo arm will be followed until 52 weeks after their last injection or until the last participant in the active study product arm completes their Week 41 visit, whichever comes first, at which time the study will be unblinded to assess the primary endpoint. From that point on, placebo participants will no longer be followed.

The protocol team will be targeting an average annual retention rate of 90 percent.

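### Placebo participants leave the study earlier than active participants, yet safety over follow-up is summarised and tested as simple proportions by arm, which biases the secondary comparison against 744LA

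*Protocol*

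**What the plan says.** Protocol 2.4.2 sets the follow-up of the active arm: "Participants in the active study product arm will be followed for 52 weeks following their last injection". With the third injection at Week 29, that is Week 81. Placebo participants are followed for the same 52 weeks or, in the words of 7.3, "until the last participant in the active study product arm completes their Week 41 visit, whichever comes first". Section 7.3 adds: "From that point on, placebo participants will no longer be followed". Section 5.16 sets the actual moment of exit later than the trigger: "Participants will be unblinded at their next study visit following final confirmation from the HPTN SDMC". Section 7.5 requires the Week 41 data to be entered, cleaned and verified first.

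For the analysis, 7.1.2 lists as a secondary endpoint the proportion with a Grade 2 or higher event in the 52 weeks after the final injection. Section 7.6.2 (Safety Endpoints) states: "Secondary safety analyses will include the same definition applied over the oral phase only (week 0 to week 5) and the aggregate oral+injectable+follow-up period". The same section prescribes, for each safety endpoint, the number and percent by arm with each participant counted once, exact binomial confidence intervals, and Fisher's exact test. It calls any p-value descriptive. Person-years appear only for HIV incidence (7.6.3).

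**The concern.** A simple proportion with an exact binomial interval treats every participant as having had the same opportunity to show an event. Over the aggregate period and the 52 weeks after the final injection, this is untrue by design, and the shortfall lies entirely in the placebo arm. Calling p-values descriptive does not help, because the tabulated percentages themselves are distorted.

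The first secondary objective is safety over the 52 weeks after the final injection. Section 1.2.4 gives safety during the long drug tail as a reason for that follow-up. The by-arm table serving this objective would show an excess on 744LA that comes partly or wholly from observation time.

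**Working it through.** **The plan's own figure.** The protocol gives no figure for the follow-up comparison. The nearest is the 82% power in 7.2 that the 95% interval for the difference has an upper limit of at most 10% when both true rates are 5% (120 against 40). Exact enumeration with the two-sided Wald interval gives 82.4%, so it reproduces. That calculation equates no drug effect with equal proportions, which is sound only when both arms have the same window.

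**Inputs from the protocol.** Accrual A of about 16 to 24 weeks (2.4.2); third injection at Week 29; visits at Weeks 41, 53, 65, 77 and 81; exit at the next visit after confirmation (5.16).

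**Assumptions, not in the protocol.** Uniform accrual; a cleaning lag L of 0, 8 or 12 weeks; all three injections received; identical hazards in both arms; a proportion p = 20% affected by Week 41; hazard after Week 41 equal to r = 100%, 50% or 25% of the earlier one.

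**Step 1: placebo exit.** At confirmation, placebo participants lie uniformly between Weeks 41 + L and 41 + A + L.
- A = 16, L = 0: between Weeks 41 and 57. A share of 12/16 = 75% exits at Week 53 and 25% at Week 65. Mean = 0.75 × 53 + 0.25 × 65 = 56.
- A = 24, L = 12: between Weeks 53 and 77. Half exit at Week 65 and half at Week 77. Mean = 71.

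Mean placebo exit is therefore Week 56-71 against 81, or 27-42 weeks after the third injection against 52.

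**Step 2: proportions under no drug effect.** For exit at week w of 41 or later, the effective weeks are 41 + r(w − 41) from Week 0, and 12 + r(w − 41) from Week 29. The proportion affected is 1 − (1 − p)^(effective weeks / 41).
- Active, r = 1: aggregate 1 − 0.8^(81/41) = 35.7%; after the final injection 1 − 0.8^(52/41) = 24.6%.
- Placebo, r = 1, A = 16, L = 0: 0.75 × (1 − 0.8^(53/41)) + 0.25 × (1 − 0.8^(65/41)) = 0.75 × 25.1% + 0.25 × 29.8% = 26.2%.
- Placebo, r = 1, A = 24, L = 12: 0.5 × 29.8% + 0.5 × 34.2% = 32.0%.

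| Tail hazard r | Aggregate, active | Aggregate, placebo | After final injection, active | After final injection, placebo |
|---|---|---|---|---|
| 100% | 35.7% | 26.2-32.0% | 24.6% | 13.6-20.4% |
| 50% | 28.3% | 23.2-26.3% | 16.0% | 10.1-13.7% |
| 25% | 24.2% | 21.6-23.2% | 11.3% | 8.2-10.1% |

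At p = 40% and r = 1, the aggregate figures are 63.5% against 50.1-58.6%. Over p = 20% and 40% and all three values of r, the aggregate gap runs from 24.2 − 23.2 = 1.0 point to 63.5 − 50.1 = 13.4 points, always against 744LA. With the same window in both arms the expected gap is zero.

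**Step 3: would events per person-year repair it?** Only if the hazard is constant. At r = 25%, A = 16, L = 0, in units of the early hazard, the active rate is (41 + 0.25 × 40)/81 = 0.630 and the placebo rate is (41 + 0.25 × 15)/56 = 0.799, a ratio of 0.79. At r = 50%, A = 24, L = 12, the rates are 61/81 = 0.753 and 56/71 = 0.789, a ratio of 0.95. A crude rate would make 744LA look falsely safer.

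**The case against.** Several points limit this, and most of them stand.

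- The primary safety endpoint, tolerability and the oral-phase analysis use windows of the same design in both arms. Section 7.2 disclaims formal comparison.
- A constant hazard to Week 81 is generous. After Week 41, blood counts, chemistry, ECGs and injection-site evaluations stop, and liver tests are the only scheduled safety laboratory tests. The lower rows of the table are at least as plausible as the first.
- Section 7.6.2 names the oral phase and the aggregate period as its secondary safety analyses. The 52-week window comes from 7.1.2 and enters the by-arm tabulation only through the rule covering each safety endpoint.
- A statistical analysis plan could add censoring rules. But the protocol itself fixes the percentage, the interval and the test, so a plan that followed it would carry the problem forward.

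A reader might also infer three stronger things, which the protocol does not support.

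- That placebo participants could lose their Week 41 data, because the trigger names only the active arm. Under 5.16 they are unblinded at their next visit. A participant less than 6 weeks behind the last active one has passed Week 35, so the next visit is Week 41. Being further behind, with uniform 24-week accrual and no cleaning lag, requires all 132 active participants to enrol in the first 18 weeks: 0.75^132, about 3 × 10⁻¹⁷.
- That 5.16 is wrong to say "it is likely that some placebo participants will complete their full follow-up visit schedule". Under 5.15 the schedule ends at Week 57 after one injection and Week 69 after two. With 24-week accrual, just over 12 weeks of cleaning takes the earliest three-injection participants past Week 77, and their next visit is Week 81.
- That placebo follow-up stops at the trigger, with a mean of 49-53 weeks (41 + 16/2 and 41 + 24/2). Sections 5.16 and 7.5 rule out immediate release.

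**Conclusion.** The point holds as a correction to a secondary analysis. Over the aggregate period and the 52 weeks after the final injection, proportions by arm with binomial intervals and Fisher's test are the wrong summary for arms that are followed for different lengths of time. The direction is known: against 744LA in expectation, though not in every realised trial.

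The size is not known. It rests on an event rate, a cleaning lag and a tail hazard that the protocol does not give. At 20% affected by Week 41, the null aggregate gap is about 4-9 points with a constant hazard and about 1-5 points with a reduced tail hazard. Nothing here touches the primary conclusions.

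**What to change.** In 7.1.2 and 7.6.2, limit the between-arm safety contrast to follow-up observed in both arms. Either stop it at Week 41, or use Kaplan-Meier cumulative incidence censored at each participant's unblinding or exit and compare arms only over the time common to both. Report active-arm data beyond that as single-arm; those data are also collected after unblinding. Do not use crude events per person-year over unequal follow-up as the main contrast.

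The unblinding trigger and the 5.16 expectation can stay as written. The cost is wording in two sections, with no change to visits, sample size or the timing of unblinding.
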